3.4.1 Lymphopenia

Both ponesimod and DMF have lymphocyte-lowering effects. Low lymphocyte counts can potentially increase the risk of infections including opportunistic infections, and need to be monitored. The mechanism and modality of lymphocyte count reduction by the two drugs are very different. DMF treatment slowly reduces lymphocyte counts by inducing apoptosis of lymphocytes with a nadir after one year of treatment. By contrast, ponesimod treatment induces lymphocyte count reduction within one week by reversible sequestration of lymphocytes in secondary lymphoid tissues. Discontinuation of DMF treatment is followed by a slow increase of lymphocyte counts over several weeks, while discontinuation of ponesimod is followed by recovery of lymphocyte counts within one week. In a 13-week treatment duration study in dogs, the combination of ponesimod with DMF induced effects on lymphocyte counts comparable to those observed with each drug alone. The effect on lymphocytes by adding ponesimod to DMF has not been investigated in humans. All these aspects represent important safety concerns that have been taken into account when designing appropriate safety measures as follows:

- To reduce the risk of high grade lymphopenia during the course of the study, only subjects with lymphocyte counts $\geq 0.8 \times 10^9/L$ ($\geq 800/mm^3$) after at least 12 months of DMF treatment or subjects with lymphocyte counts $\geq 0.9 \times 10^9/L$ ($\geq 900/mm^3$) after at least 6 months of DMF treatment (but < 12 months) will be enrolled [see inclusion criterion #8 in Section 4.3].
- To ensure a relatively stable effect of DMF on lymphocyte has been reached prior to study entry, subjects with large excursions in lymphocyte counts between screening and baseline assessments (at least 3 weeks apart) will not be included [see inclusion criterion #8 in Section 4.3].

- To ensure a prompt detection of high grade lymphopenia or unstable declining lymphocyte counts while on DMF or after adding ponesimod to DMF, lymphocyte counts will be monitored every 4 weeks (\pm 3 days) during the initial 24 weeks, and then every 12 weeks for the remainder of the study.

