 - A total lymphocyte count decrease of $> 50\%$ from the value recorded at Visit 5 (Week 4) associated with a total lymphocyte count $< 0.5 \times 10^9/L$ ($< 500 \text{ cells/mm}^3$) is recorded at 2 consecutive scheduled visits after Visit 5 (Week 4). In this event, an alert containing the lymphocyte count result will be sent to the principal investigator / treating neurologist and the sponsor.
 - A total lymphocyte count $< 0.5 \times 10^9/L$ is observed at FU. In this event, an alert containing the total lymphocyte count result will be sent to the principal investigator / treating neurologist. Discontinuation of DMF treatment should be considered in accordance with prescribing information [[Tecfidera USPI](#), [Tecfidera SmPC](#)].
 - WBC and total lymphocyte counts measured at any of the visits in the PTOP. For subjects who have entered PTOP following study drug discontinuation,

lymphocyte count values recorded after entering the PTOP will be visible to the principal investigator / treating neurologist.

- All MRI scans collected for the assessment of efficacy endpoints are evaluated by a central reading center (MIAC) also in a fully blinded fashion.
Under no circumstances should potentially unblinding information be shared with the efficacy assessor.

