5.1.12.2 Hematological abnormalities

Subjects **must** be permanently discontinued from study drug at any time throughout the study if one of the following occurs:

- Confirmed total lymphocyte count decrease of > 50% from the value recorded at Visit 5 (Week 4) associated with a total lymphocyte count $< 0.5 \times 10^9/L$ ($< 500 \text{ cells/mm}^3$) at 2 consecutive scheduled visits after Visit 5 (Week 4)
- Confirmed total lymphocyte count $< 0.2 \times 10^9/L$ ($< 200 \text{ cells/mm}^3$)

Confirmation will be done as follows:

Whenever one of the above conditions is met, an alert will be sent by the central laboratory to the principal investigator and the sponsor. The principal investigator will immediately contact the subject and ask her/him to return to the site either within 2 weeks if the total lymphocyte count is $< 0.5 \times 10^9/L$ but $\geq 0.2 \times 10^9/L$ or within 48 hours at the latest if the total lymphocyte count is $< 0.2 \times 10^9/L$ to repeat the test at trough level (pre-dose) by the central laboratory (unless the clinical situation mandates immediate local testing). If the repeat test confirms that one of the above conditions is met, then the study drug must be discontinued.

Lymphocyte counts must be monitored at least once a week by the central laboratory until the lymphocyte count has returned to $\geq 0.8 \times 10^9/L$ or $\geq 80\%$ of the value recorded at Visit 2 (Baseline). Any clinically relevant finding meeting the definition of an AE will be recorded accordingly in the eCRF.

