7.3.13 Laboratory assessments

7.3.13.1 Type of laboratory

A central laboratory (see central laboratory manual for contact details) will be used for all protocol-mandated laboratory tests, including re-tests due to laboratory abnormalities and laboratory tests performed at unscheduled visits. Central laboratory data will be automatically transferred from the central laboratory database to Actelion's clinical database.

Under specific circumstances (e.g., if the subject lives far from the site and cannot return every 4 weeks (\pm 3 days) for the lymphocyte count assessments), laboratory samples may be collected at a laboratory close to where the subject lives (satellite laboratory), and sent to the central laboratory for analysis. In such a case, the satellite laboratory must be provided with the central laboratory sampling kits, which must be used for blood collection. The blood samples collected locally will be shipped by the local laboratory to the central laboratory for analysis. Such a local laboratory shall be identified as soon as possible, but no later than upon enrollment of the subject in the study.

In exceptional cases (e.g., subject is hospitalized in a different hospital from the study center due to a medical emergency, or missing central laboratory values) local laboratory results (with the corresponding normal ranges) will be entered into the clinical database via dedicated CRF pages.

If a central laboratory sample is lost or cannot be analyzed for whatever reason, the investigator may collect an additional sample as soon as possible for retest analysis, unless a local laboratory sample was collected within the same time-window and these test results are available.

The central laboratory will provide all laboratory results by fax or email to the site with the exception of the results of the total WBC count and total lymphocyte count. The lymphocyte count results obtained during treatment period will be communicated to the site only if one of the below applies:

- A total lymphocyte count $< 0.2 \times 10^9/L$ is recorded by the central laboratory. In this event, an alert containing the total lymphocyte count result will be sent to the principal investigator / treating neurologist and the sponsor [see Section 5.1.12.2].

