8.2 Treatment period

The treatment period consists of the post-dose assessments at Visit 3 to Visit 18 (Randomization Day 1, Weeks 2, 4, 12, and every 12 weeks thereafter until EOT).

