8.2.2 Four-weekly lymphocyte counts

Lymphocyte counts will be assessed every 4 weeks up to Week 24 (i.e., additional lymphocyte tests will be performed at Week 8, Week 16, and Week 20). (Thereafter, lymphocyte counts will be assessed every 12 weeks up to EOT.)

The test window is \pm 3 days. Under specific circumstances (e.g., subject lives far away from the site and cannot return every 4 weeks), laboratory samples could be drawn in a local laboratory close to where the subject lives, and analyzed at the central laboratory [see Section 7.3.13].

8.2.3 Visit 4 – Day 15

The visit window for this visit is \pm 1 day. The visit includes:

- MS relapse.
- Health care resource utilization since the last visit.
- Recording of changes in concomitant medications.
- Body temperature.
- SBP/DBP (pre-dose).
- 12-lead ECG (pre-dose).
- Hematology (including lymphocytes), blood chemistry.
- Assessment and recording in the eCRF of methods of contraception (for WOCBP only).
- Urine pregnancy test for WOCBP.
- Recording of AEs and SAEs.
- Study treatment accountability and compliance review.
- IRT call and study treatment dispensing.
- Remind WOCBP to use the methods of contraception defined for this study. The reminders must be documented in the hospital chart.

- Schedule an appointment for next visit and instruct subject to:
 - bring back any blister packs (used, partially used and unused blister packs) and any unused tablets.
 - not take study treatment on the day of study visit prior to coming to the site.
 - contact their principal investigator / treating neurologist at the clinical site immediately in the event of the appearance of any symptoms suggestive of an MS exacerbation.

8.2.4 Visit 5 – Week 4

The visit window for these visits is \pm 5 days. The visits include:

- Recording of changes in concomitant medications.
- Assessment and recording in the eCRF of methods of contraception (for WOCBP only).
- SBP/DBP (pre-dose).
- 12-lead ECG (pre-dose).
- MS relapse.
- Health care resource utilization since the last visit.
- Body temperature.
- Hematology (including lymphocytes), blood chemistry.
- Urine pregnancy test for WOCBP.
- Recording of AEs and SAEs.
- Study treatment accountability and compliance review.
- IRT call and study treatment dispensing.
- Remind WOCBP to use the methods of contraception defined for this study. The reminders must be documented in the hospital chart.
- Schedule an appointment for next visit and instruct subject to:

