Hematocrit (L/L)	< 0.28 (female) < 0.32 (male)	< 0.20	> 0.55 (female) > 0.60 (male)	> 0.65
Platelet count (10^9 /L)	< 75	< 50	> 600	> 999
RBC count (10^{12} /L)	ND	ND	ND	ND
WBC count (10^9 /L)	NA	< 1.9	> 20.0 ALERT: > 20.0	> 100.0
Lymphocyte (10^9 /L)	ND	< 0.2 ALERT: < 0.2 Decrease of > 50 % from the value of total lymphocyte count recorded at Visit 5 (Week 4) associated with a total lymphocyte count < 0.5×10^9/L recorded at two consecutive visits after Visit 5 (Week 4)	> 4.0	≥ 8
Neutrophils (10^9 /L)	< 1.5	< 1.0	ND	ND

Parameter (SI unit)	LL	LLL	HH	HHH
Eosinophils (10^9 /L)	ND	ND	> 5.0	ND
Monocytes (10^9 /L)	ND	ND	ND	ND
Basophils (10^9 /L)	ND	ND	ND	ND
Polymorphonuclear leucocyte/Band cells (%)	ND	ND	> 90%	> 95%
AST (U/L)*	ND	ND	≥ 3 ULN ALERT: ≥ 3 ULN	≥ 5 ULN ALERT: ≥ 5 ULN ≥ 8 ULN
ALT (U/L)*	ND	ND	≥ 3 ULN ALERT: ≥ 3 ULN	≥ 5 ULN ALERT: ≥ 5 ULN ≥ 8 ULN
Total bilirubin (umol/L)	ND	ND	≥ 2 ULN ALERT: ≥ 2 ULN combined with ALT or AST ≥ 3 ULN	≥ 5 ULN
Alkaline Phosphatase (U/L)	ND	ND	> 2.5 ULN	> 5 ULN
INR*	ND	ND	> 1.5 ULN or > 1.5 times above baseline if on anticoagulation ALERT: > 1.5 combined with ALT or AST ≥ 3 ULN	> 2.5 ULN or > 2.5 times above baseline if on anticoagulation
Lactate dehydrogenase	ND	ND	ND	ND
Creatinine (umol/L)*	ND	ND	>1.5 ULN or >1.5 x baseline	> 3 ULN or >3 x baseline
Creatinine clearance (mL/min)	< 60	< 30	ND	ND
Urea (mmol/L)	ND	ND	> 2.5 ULN	> 5 ULN

Confidential

Parameter (SI unit)	LL	LLL	HH	HHH
Albumin (g/L)	< 30	< 20	ND	ND
Protein total (g/L)	ND	ND	ND	ND
C-reactive protein (mg/L)	ND	ND	ND	ND
Glucose (mmol/L)	< 3.0	< 2.2	> 8.9	> 13.9
Potassium (mmol/L)	< 3.2	< 3.0	> 5.5	> 6.0
Sodium (mmol/L)	ND	< 130	> 150	> 155
Calcium (mmol/L)	< 2.0	< 1.75	> 2.9	> 3.1
Chloride (mmol/L)	ND	ND	ND	ND
Triglyceride (mmol/L)	ND	ND	> 3.42	> 11.4
Cholesterol (mmol/L)	ND	ND	> 7.75	> 12.92
Serum pregnancy test	ND	ND	ND	Positive ALERT: Positive

* HH and HHH based on CTCAE 2010 v4.03 [[CTCAE 2010](#)]. An ALERT will be sent when INR \geq 1.5 based on the guidance for monitoring liver test abnormalities from FDA [[FDA 2009b](#)]

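### Read literally, the Week 8, 16 and 20 lymphocyte counts cannot trigger the decline limb of the stopping rule, and a confirming repeat of 0.2 to < 0.5 × 10⁹/L is on neither release list

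*Protocol*

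**What the plan says.** Section 3.4.1 of the Protocol gives the reason for the 4-weekly counts in the first 24 weeks: "To ensure a prompt detection of high grade lymphopenia or unstable declining lymphocyte counts while on DMF" or after ponesimod is added. Section 8.2.2 spells out what this adds to the visit schedule: "additional lymphocyte tests will be performed at Week 8, Week 16, and Week 20". Section 8.2 lists the treatment-period visits as "Visit 3 to Visit 18 (Randomization Day 1, Weeks 2, 4, 12, and every 12 weeks thereafter until EOT", so none of those three weeks is a numbered visit. Under 7.3.13.1 and 8.2.2 the samples may be drawn away from the site in specific circumstances.

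Section 5.1.12.2 has two limbs for mandatory permanent discontinuation:

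- a confirmed count below 0.2 × 10⁹/L, not tied to any visit;
- a confirmed fall of more than 50% from the Week 4 value with a count below 0.5 × 10⁹/L, found "at 2 consecutive scheduled visits after Visit 5 (Week 4".

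The alert trigger in 5.1.4.2 uses the same unit, "recorded at 2 consecutive scheduled visits after Visit 5 (Week 4", and so does 7.3.13.1. Appendix 6 drops the word scheduled: "two consecutive visits after Visit 5 (Week 4".

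Stopping then depends on a repeat: "If the repeat test confirms that one of the above conditions is met, then the study drug must be discontinued". On-treatment counts are otherwise withheld from the site. Section 7.3.13.1 says "The lymphocyte count results obtained during treatment period will be communicated to the site only if one of the below applies", and 5.1.4.2 carries a parallel list. After an alert, 5.1.12.2 also requires at least weekly counts until the value recovers to 0.8 × 10⁹/L or to 80% of the Visit 2 value.

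**The concern.** The unit in which counts are monitored and the unit in which the decline limb is triggered are not the same. Three of the planned early counts fall between visits, so on the literal wording they cannot contribute to the limb that deals with a falling count. This affects only the window that the extra counts were added to cover.

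The confirmation step has a related gap. The person who must stop the drug has to know the repeat result, yet a repeat taken at an unscheduled return is not a scheduled-visit finding. If it lies between 0.2 and 0.5 × 10⁹/L, it meets no listed condition for release.

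The Protocol itself says that the effect of this combination on lymphocytes has not been investigated in humans (3.4.1), and that most reported PML cases on DMF were associated with sustained lymphopenia (1.5, 3.4.2). A mandatory safety rule in that setting should be executable from its text. A central laboratory that programs alerts from 5.1.12.2 and one that programs them from Appendix 6 could build different triggers.

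**Working it through.** **Inputs.** Visits after Week 4: Weeks 12, 24, 36, 48 and so on (8.2). Planned counts after Week 4: Weeks 8, 12, 16, 20 and 24, then every 12 weeks (3.4.1, 8.2.2). Decline limb: two consecutive qualifying findings (5.1.12.2).

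**Plan's own figure.** Table 7 lists 3 lymphocyte-only tests. The 4-weekly counts after Week 4 up to Week 24 are {8, 12, 16, 20, 24}. Removing the visit weeks {12, 24} leaves {8, 16, 20}, which is 3 tests. The figure is reproduced.

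**Earliest possible trigger.** With numbered visits only, the first two are Weeks 12 and 24, so Week 24. With all planned counts, the first two are Weeks 8 and 12, so Week 12. The difference is 24 − 12 = 12 weeks.

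**Delay by the week in which the count first qualifies.** The trigger week is the second qualifying time point at or after first detection. Assumptions: once low, the count stays low; weeks are nominal and visit windows are ignored.

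| First low at | Visits only | All planned counts | Delay (weeks) |
|---|---|---|---|
| Week 8 | Week 24 | Week 12 | 12 |
| Week 12 | Week 24 | Week 16 | 8 |
| Week 16 | Week 36 | Week 20 | 16 |
| Week 20 | Week 36 | Week 24 | 12 |
| Week 24 | Week 36 | Week 36 | 0 |
| Week 36 | Week 48 | Week 48 | 0 |

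The repeat test, allowed up to 2 weeks for counts of 0.2 to < 0.5, comes after the trigger under either reading and so adds nothing to the difference.

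**Release of the repeat result.** The items in 5.1.4.2 and 7.3.13.1 are: any central count < 0.2; a WBC count > 20 or lymphocytes > 8.0; the decline finding at two consecutive scheduled visits; a count < 0.5 at FU; and counts at PTOP visits. Set against these:

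- repeat < 0.2: released under the first item, whatever the visit;
- repeat of 0.2 to < 0.5 at an unscheduled return during treatment: no item applies;
- weekly counts after stopping: unclear. The restriction is worded for the treatment period, which under 3.5.2 ends at premature discontinuation, but both lists also carry FU and PTOP items, which would be unnecessary if later counts were freely available.

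**The case against.** The strongest reply is that this is ambiguity, not impossibility. The term scheduled visit is nowhere defined. The 4-weekly counts have their own subsection and ± 3-day window inside the schedule-of-visits chapter. Drawing them elsewhere is the exception, so subjects are normally expected to return, and Appendix 6 omits scheduled. This stands as far as it goes: the conclusion holds on the literal wording only. But if tests were meant to count, the text still needs changing in three sections.

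A reader might infer three stronger things that the documents do not support.

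- *That the extra counts serve no stopping rule.* They can trigger the < 0.2 limb at any week, and high-grade lymphopenia is one of the two aims in 3.4.1. The IDMC also reviews unblinded lymphocyte data about every 4 months, although that does not replace a rule for the individual subject.
- *That the result mandating a stop never reaches the site.* A repeat < 0.2 is released. For 0.2 to < 0.5, section 5.1.12.2 says that an alert follows whenever a condition is met, which can be read to cover a confirming repeat, and it allows local testing when the clinical situation demands it. What weakens that reading is that the decline condition is itself defined by scheduled visits.
- *That the site cannot follow recovery, or would take a lost sample for a negative one.* The first is not established, given the treatment-period scope of the restriction. Against the second, 7.3.13.1 lets the investigator redraw a lost sample, which presupposes that the site is told.

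**Conclusion.** The point holds in a limited form. On the literal wording of 5.1.4.2, 5.1.12.2 and 7.3.13.1, the decline limb cannot fire before Week 24, against Week 12 if planned tests qualify. The delay is 8 to 16 weeks for persisting declines first detected at Weeks 8 to 20, and nil from Week 24. This rests on nominal weeks, on a count that stays low, and on scheduled visits meaning the numbered visits. The < 0.2 limb is not affected.

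Separately, neither exclusive release list has an item for a confirming repeat of 0.2 to < 0.5 × 10⁹/L taken at an unscheduled return. The status of the weekly follow-up counts is unclear rather than demonstrably wrong.

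No number of affected subjects can be derived, because the Protocol gives no expected rate of such declines. Nothing here bears on sample size, power or type I error, and no view is taken on the thresholds or on which trigger is clinically right.

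**What to change.** Reconcile 3.4.1, 5.1.4.2, 5.1.12.2, 7.3.13.1, 8.2.2 and Appendix 6 on which counts qualify for the decline limb, and use one wording throughout. Which trigger to adopt is a clinical decision for the sponsor.

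In the release lists of 5.1.4.2 and 7.3.13.1, add an item for subjects who have already had an alert. It should cover the confirmatory repeat result, whatever its value, and the follow-up counts that 5.1.12.2 requires.

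The cost is Protocol wording and a change to the central laboratory's alert programming. The blinding cost is small, because it is confined to subjects for whom a lymphocyte value has already been released.

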5.1.12.3 General guidance for monitoring of subjects for opportunistic infections during treatment

Heightened vigilance is required for opportunistic infections caused by virus, fungi and bacteria. In the event of an opportunistic infection, the subject must permanently

discontinue the study drug and must be referred to an expert in infectious diseases for further examination and treatment. Early antiviral treatment will be considered.

Opportunistic infections caused by the reactivation of human herpes viruses (herpes simplex viruses, varicella-zoster virus, Epstein-Barr virus, cytomegalovirus) may be primarily associated with neurological symptoms. The neurotropic herpes viruses (herpes simplex and varicella-zoster) are frequent human pathogens and their reactivation can cause serious infections of the CNS such as encephalitis and meningitis. The most frequent characteristics of these infections are an acute onset, associated with fever, headache, confusion, personality changes, and disorientation. Any suspicion of these infections must lead to immediate interruption of study drug treatment and to early initiation of antiviral treatment [[Steiner 2007](#)].

The thorough physical examination and blood tests on the routine visits should be focused on any potential sign of skin, mucosal surfaces, gastrointestinal tract, liver, hematological etc., abnormality and organ dysfunction suggesting a potential opportunistic infection.

Subjects should be advised to be proactive and alert in reporting any unusual neurological symptoms and any signs and symptoms indicative of systemic infections, such as fever, malaise and fatigue [[Kappos 2007](#)].

The diagnostic workup and management of subjects with suspicion of opportunistic infection accompanied by CNS symptoms is described in Section [5.1.12.3.1](#).

5.1.12.3.1 Guidance for screening, exclusion and on-treatment monitoring of subjects for progressive multifocal leukoencephalopathy / other opportunistic CNS infections

Subjects with known PML infection or evidence of new neurological symptoms or MRI signs within 6 months prior to randomization, which are compatible with a diagnosis of PML infection, will not be eligible for the study. Subjects in whom suspicion of PML or other opportunistic CNS infections has been raised after randomization by new or worsening neurological symptoms combined with results of objective neurological exam or by MRI findings will have the study drug and DMF interrupted, and will be referred to the local MRI department to perform MRI as described in Section [7.2.3](#) which will be reviewed by the MRI safety board [see Section [3.8.3](#)]. The suspicion of PML or other opportunistic CNS infections will be raised if the subjective and objective findings cannot readily be explained by the subject's MS (e.g., a relapse) or another known condition (e.g., abnormal speech due to a dental intervention or limb weakness due to a trauma) not corresponding to exclusion criteria or if signs of PML / other opportunistic CNS infection are present on MRI. The additional diagnostic workup may include lumbar puncture for cerebrospinal fluid (CSF) analysis including test for JCV in CSF. If, based on the results

of the MRI safety board review, other diagnostic tests and clinical symptoms and signs, the suspicion of PML or other opportunistic CNS infections can be ruled out, the investigator will consider re-start of the study drug if the risk/benefit is still considered positive for the subject and if criteria for permanent discontinuation of the study drug have not been met. **NB:** In subjects with suspicion of acute CNS infection, early lumbar puncture and antiviral treatment should be considered.

Progressive multifocal leukoencephalopathy (PML) is an opportunistic infection of the CNS that can lead to death or severe disability. Active replication of the human polyoma JCV in glial cells of the brain, causing lytic death in oligodendrocytes, is the underlying pathobiology of PML. The infection typically arises in severely immunocompromised subjects, e.g., those with HIV infection, malignant disease, or transplanted organs. People with autoimmune rheumatic diseases, especially systemic lupus erythematosus, are also at higher risk of PML [Kappos 2011].

As mentioned in Section 3.4.2, MS subjects treated with natalizumab are at increased risk of developing PML. In addition to natalizumab, cases of PML have been reported in subjects treated with various drugs, usually in combination with corticosteroids, including alkylating agents (e.g., cyclophosphamide, carmustine, and dacarbazine), purine analogues (e.g., fludarabine, cladribine, and azathioprine), immunosuppressants (e.g., cyclosporin, tacrolimus, sirolimus, and mycophenolate), and therapeutic monoclonal antibodies (e.g., rituximab, infliximab, etanercept, basiliximab, daclizumab, efalizumab, alemtuzumab, and muromonab-CD3) [Kappos 2011]. Sporadic cases of PML have occurred in patients treated with DMF [FDA 2015] and with fingolimod [Gilenya USPI]. The diagnosis of PML is based on a combination of clinical, imaging and laboratory findings according to the consensus statement from the American Academy of Neurology published in 2013 [Berger 2013]. Among the common clinical findings are motor weakness, gait abnormalities, visual field deficits, speech and language disturbances, and incoordination. Sensory loss, seizures, headache, and diplopia occur less frequently. Although all these symptoms can be due to MS relapse, the time course often helps to distinguish PML from MS. While MS relapses tend to occur over hours to days, normally stabilize, and can resolve without treatment, PML tends to be progressive over days to weeks [Chalkley 2013].

In a retrospective study of MRI scans in 40 patients with MS treated with natalizumab and PML [Yousry 2012] the characteristic pattern of early PML lesions included:

- Subcortical localization
- MRI signal: T2- and DW-hyperintense and T1-hypointense lesions;
- Lesion border: sharp toward the grey matter and ill-defined toward the white matter.

In all but one patient the discrimination between new PML lesions and MS lesions could be done without problems.

The most useful laboratory finding for PML is demonstrating the presence of JCV in CSF using polymerase chain reaction (PCR). The sensitivity of the newer ultrasensitive techniques is 95% and the method is highly specific. However, a negative JCV PCR result should not exclude a possible diagnosis of PML.

Based on these three criteria (clinical, MRI and CSF), the diagnostic certainty of PML can be categorized into definite (all three criteria positive), probable (two out of three criteria positive), possible (one out of three criteria positive) and not PML (all criteria negative). Subjects with probable PML should be managed as those with definite PML.

Case 1: At Visit 1 (Screening).

The subjects in whom the suspicion of PML / other opportunistic CNS infection has been raised by the investigator based on evidence of new neurological symptoms or MRI signs within 6 months prior to Visit 1 (Screening), which are compatible with a diagnosis of PML infection, will have MRI performed as described in Section 7.2.3, and reviewed by the MRI safety board. Based on the relevant clinical findings, results of MRI review, and, if justified and indicated, CSF analyses, the investigator will determine the probability of PML. Only subjects in whom PML/other opportunistic CNS infection can be ruled out will be eligible for the study. Subjects with possible PML at Visit 1 (Screening) in whom this diagnosis has been later ruled out will be eligible for a single re-screening.

Case 2: Subject randomized in the study, coming to scheduled visits.

The subjects in whom the suspicion of PML/other opportunistic CNS infection has been raised by the investigator as described above, will have the study drug and DMF interrupted and will have MRI performed as described in Section 7.2.3, and the site can ask for a review of the MRI by the MRI safety board [see Section 3.8.3]. Further diagnostic workup (such as lumbar puncture for JCV) will be performed at investigator's discretion. Based on the relevant clinical and nonclinical findings, including the MRI evaluation by the MRI safety board if applicable, the investigator will determine the probability of PML/other opportunistic CNS infection. Subjects in whom PML/other opportunistic CNS infection can be ruled out will be eligible for re-start of the study medication. Subjects with definite or probable PML or diagnosis of other opportunistic CNS infection will have the study drug and DMF permanently discontinued and will be managed according to the local practice (e.g., immune reconstitution and high dose corticoids). Subjects with possible PML/other opportunistic CNS infection will be observed off-study drug and assessed with repeated clinical, imaging and/or laboratory exams at the investigator's discretion until the PML/other opportunistic CNS infection

has been ruled out or confirmed. The study drug may be re-started if PML / other opportunistic CNS infection has been ruled out at a later time point.

Case 3: Subject randomized in the study, reporting new or worsening neurological symptoms outside the scheduled visits.

In case a subject contacts the investigator because of new or worsening neurological symptoms, the investigator should see the subject at an unscheduled visit as soon as possible and perform a full neurological exam in order to decide if the symptoms can be explained by a relapse or can be otherwise explained, or if suspicion of PML/other opportunistic CNS infection should be raised. If the findings indicate a relapse, the subject will be referred to the efficacy assessor for EDSS assessment. If the findings raise suspicion of PML/ other opportunistic CNS infection, the subject will have the study drug and DMF interrupted and will have MRI performed as described in Section 7.2.3, and the site can ask for a review of the MRI by the MRI safety board. Further diagnostic workup (such as lumbar puncture for JCV) will be performed at investigator's discretion. The further process will be the same as for Case 2 above.

Case 4: MRI from a scheduled visit shows findings not typical for MS.

In case the MRI at a scheduled visit shows signs atypical for MS, detected by the neuroradiologist or during the central review by the MIAC, the site and the sponsor will be alerted and the site can ask for a review of the MRI by the MRI safety board. The subject will be invited for an unscheduled visit at which the investigator will interview the subject for neurological signs and symptoms and perform a full neurological exam. In the event of suspicion of PML, the study drug will be interrupted. Based on the full evaluation of the subject, relevant clinical findings and results of any additional investigations, such as lumbar puncture for JCV, the investigator will determine the probability of PML/other opportunistic CNS infection. Subjects in whom PML/other opportunistic CNS infection can be ruled out will be eligible for re-start of the study medication. Subjects with definite or probable PML or diagnosis of other opportunistic CNS infection will have the study drug and DMF permanently discontinued and will be managed according to the local practice (e.g., immune reconstitution and high dose corticoids). Subjects with possible PML/other opportunistic CNS infection will be observed off-study drug and assessed with repeated clinical, imaging and/or laboratory exams at the investigator's discretion until the PML/other opportunistic CNS infection has been ruled out or confirmed. The study drug may be re-started if PML / other opportunistic CNS infection has been ruled out at a later time point.

